1 Principal investigator; 3 Co-Investigators; 1 Care Manager; 1 Research Coordinator; 2 Research Assistants

6. Will specially obtained software be used? Yes - See below No

6.1. If yes, describe the software, the source of the software, whether a license will be required and who will fund the license, as well as any data that will be stored in temporary files on the computer's hard drive.

7. Will any web-based applications be used? Yes - See below No

7.1. If yes, identify the application and its security features. Indicate how it will be used, e.g., for recruiting subjects, completing questionnaires, or processing data.

REDCap; the VA approved web-based application can only be accessed on the VA Intranet and requires a log-in for each user. It will be used for completing questionnaires. We also will use Qualtrics for completing questionnaires/entering research assessment data. Only coded data will be used in these applications (PHI will not be entered or stored).

8. How will electronic data and/or paper records be secured? If data is being stored on a computer hard drive, indicate if it is encrypted per VA guidelines.

Electronic research records will be stored on the MIRECC server. Paper records will be secured in locked cabinets in the CHERP suite in the [name] or at the Center for Integrated Healthcare (CIH); VA Western New York - Buffalo [name].

NOTE: Electronic research records should be stored/secured on the Research and Development server (Z drive), MIRECC server, PADRECC server or CHERP server.

9. Will mobile devices be used in the study, i.e., laptops, audio recorders? Yes No

9.1. If yes, indicate that mobile devices will be encrypted and that the encryption is FIPS 140-2 validated.

The recorder we use is encrypted and it is FIPS 140-2 validated.

10. How will data be transmitted and/or shipped, and how will it be protected during transmission or shipping?

N/A

11. How will project research data be stored?

11.1. Indicate precisely where data will be stored to include physical site, network location/server name, type of mobile storage device, building and room number etc.

*Paper data – CHERP suite, [name]; VAWNY CIH, [name]
Electronic data – MIRECC server*

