Aim 1 Hypotheses: We hypothesize that, compared to CGs in UC, CGs in the intervention arm will have significantly less distress (Hyp. 1a), and a better ability to function effectively in their work and CG roles (Hyp. 1b).

Aim 2 Hypotheses: We hypothesize that relative to those in UC, CGs assigned to the intervention arm will have higher levels of physical and emotional well-being (Exploratory Hyp. 2a). We also hypothesize that CGs/CRs in the intervention arm will report higher utilization of needed services (e.g., CR MH and primary care and CG-related services) (Exploratory Hyp. 2b).

3. Resources and Personnel

3.1. Include where and by whom the research will be conducted.

Study procedures will take place at the CMCVAMC's Mental Illness, Research, Education, and Clinical Center (MIRECC), VA HSR&D Center for Health Equity Research and Promotion (CHERP), and the VAWNYHS Center for Integrated Healthcare (CIH). All telephone-delivered components of the study (i.e., recruitment, screening, research assessments, care management calls) and completion of mailed/e-mailed CG assessment packets (in cases where CGs prefer to complete the packet themselves at home) will take place in the participants' homes. The sample will be recruited from the CMCVAMC's Primary Care-Mental Health Integration program (i.e., the Behavioral Health Laboratory (BHL)), both VA sites' Mental Health Clinics and CSPs, and via VINCI. Tufts researchers will administer the SOS CM training and supervision procedures telephonically. Each site and team contribute to the overall feasibility of implementing the study; they have experience recruiting CG intervention study participants, a history of successful collaboration, and, in the CMCVAMC and VAWNYHS, the ability to provide a representative sample of Veterans with depression, anxiety, TBI, and/or PTSD and their CGs.

Randomization group will be assigned by the PI, Research Coordinator, or Biostatistician. Screening, research assessments, and chart reviews will be conducted by the Research Assistants and Research Coordinator (and, where appropriate, Care Manager). Care management will be provided by Care Managers. Supervision will be provided by Drs. [name], [name], and [name] and [name]. Data collection and quality assurance activities will be conducted by the Research Assistants and Research Coordinator, PI, and Biostatistician, respectively. Data analyses will be conducted by the Biostatistician and PI.

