4.3 Study Design

4.3.1 Describe experimental design of the study. Include sequential and/or parallel phases of the study, including durations, and explain which interventions are standard of care.

A. Overview

We will conduct a prospective, longitudinal, randomized control trial (RCT) with (n=300) CGs randomly assigned in equal proportion to the experimental CG SOS Program or a usual care (UC) arm. CGs will include employed, informal CGs of Veterans with depression, anxiety, PTSD, and/or TBI, who themselves screen positive for psychological distress and work performance limitations due to caregiving. CGs will be involved in providing regular assistance with IADLs. Following referral, recruitment, consent, and screening, eligible CGs will be surveyed at pre-intervention baseline, with post-intervention follow-ups at 4 and 9 months. Research data will be obtained from self-report telephone interviews using validated tools (with a mail/email version option) and chart-review of clinical patient record data from the VA Informatics and Computing Infrastructure (VINCI). SOS care managers (CMs) will provide the intervention telephonically. Neither the SOS nor the UC group will be restricted in its use of VA or non-VA care. Our proposed study design and methods were chosen to minimize known weaknesses in the extant, primarily observational CG research.⁵⁴ We use a pre/post randomized design, well-validated, CG-reported measures to capture the primary and secondary outcomes of psychological distress (K10 Psychological Distress Scale)^{20,21} and CG work functioning (the C-WLQ),²² rigorous eligibility criteria, and a realistic intervention approach reflecting CG input with a clear intervention goal.

B. Study Procedures

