B.1 Screening, Baseline and 4 and 9 month Follow-up Research Assessment Procedures: Once the CG is identified (by self-referral, VA providers, or VINCI), indicates an interest in study participation, and consents (in-person or by phone), the RA will complete the initial screening and, if the CG is eligible, the baseline research assessment. Next, to ensure blinding of the RAs, the Project Coordinator will use a random number table to inform each CG of their group assignment. Procedures for the assigned study arm will commence (see B.2 and B.3). All CGs will be contacted again for 4- and 9-month follow-ups, at which point the majority of baseline assessments will be re-administered. Before each assessment, RAs will remind CGs not to disclose their assigned study arm. Data on care recipients' (CRs') health and service utilization will be extracted from the CRs' clinical record via VINCI, while CG VA and non-VA CG/CR health

and service utilization will be captured by CG assessment. All research assessments (including follow-ups) will be completed by the RA by telephone (with an email/mail-in option, if preferred) and include validated questionnaires regarding CR- and CG-level sociodemographic, clinical, work- related, and psychosocial variables (Appendix 1; Table 1). In-depth qualitative interviews will be conducted at 4-month follow-up with a subgroup of CGs (n=30) from the SOS arm.

These qualitative interviews will be audio recorded.

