In order to utilize Veterans' medical records for the purpose of identifying potentially eligible participants and recruitment, we are requesting a waiver of all elements of informed consent for Veterans, including HIPAA. We also are requesting a waiver of informed consent/HIPAA in order to extract Veterans' medical record data for research purposes. Without the waiver, we cannot verify the Veterans' diagnoses or extract and analyze clinical data, as only their CGs are consented and enrolled. Moreover, without access to Veterans' names, phone numbers, and addresses prior to their assent, we cannot contact potentially eligible participants for the initial screening and assent process.

We are also requesting a waiver of documentation of informed consent and HIPAA for study/intervention takes place primarily via phone and mail, we would like to obtain oral consent for the convenience of the CGs and to expedite the enrollment process. CG consent for participation in this study will be obtained either in person or over the phone. Informed consent procedures comply with current standards of the Institutional Review Boards at the CMCVAMC and VAWNYHS. After telephone discussion of the information in the consent form, and encouraging the asking of questions/concerns, the CG will be asked if s/he gives consent to enrolled in the study. The Research Coordinator/RA will be using an IRB approved script as well as a checklist to ensure each element of consent is covered. Interested CGs will be mailed a

copy of the verbal informed consent script. CGs also will receive a Copy of Notice of Privacy Practices, and acknowledgement of its receipt will be noted. In all cases, the investigators view the process of informed consent as an ongoing process that continues throughout participation in the study.
The electronic ICF data will be kept separate from any coded, de-identified data. Following the consent and baseline process, CGs will be randomized to either usual care or Caregiver SOS using a random number table.

6.2 Describe who will be obtaining informed consent, if applicable, and any circumstances that may need to be addressed (e.g. subjects with impaired decision making ability and the use of a legally authorized representative, etc.)

The Research Coordinator and Research Assistants (and, if needed, Care Manager) will be obtaining informed consent.

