13.1. Include plan for ensuring all required local site approvals are obtained and notifying the Director of any facility where the research is being conducted but the facility is not engaged.

This is a two-site study. We have conducted intervention trials in collaboration with the VA NYHHS CIH before (including a current two-site caregiver study). During weekly meetings, staff will discuss any IRB-related activities (approvals, modifications, reporting etc.) and discuss recruitment and enrollment numbers.

13.2. Include plan for keeping all engaged sites informed of changes to the protocol, informed consent, and HIPAA authorization.

We will discuss any changes to the protocol, IC, and HIPAA procedures during weekly meetings, and have all IRB documents shared on a shared VA server. This has been effective in managing and tracking procedures and changes across our two sites in past trials.

13.3. Include plan for informing local sites of any Serious Adverse Events, Unanticipated Problems, or interim results that may impact conduct of the study.

All serious adverse events and non-serious unexpected events will be reported to the PI and IRB in accordance with Good Clinical Practice Guidelines and IRB Regulations. Severe adverse events (SAEs) (e.g., hospitalization, death), will be reported to the PI within 24 hours and to the IRB within 48 hours. Unexpected adverse events will be reported to the IRB within 72 hours. Minor and anticipated adverse events and problems will be logged and reported in the annual/continuing review to the IRB.

13.4. Include plan for ensuring the study is conducted according to the IRB-approved protocol.

The PI and Research Coordinator will routinely evaluate and assess data quality and adherence to the IRB-approved protocol. Updates and issues will be discussed during weekly team meetings.

13.5. Include plan for notifying all local facility directors and LSIs when a multi-site study reaches the point that it no longer requires engagement of the local facility (e.g., all subsequent follow-up of subjects will be performed by the PI from another facility).

We will discuss updates and enrollment numbers during weekly calls.

14. References (bibliography of cited literature)

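### Randomisation uses a random number table with no described concealment, and one permitted assigner may also recruit and assess outcomes

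*Combined protocol and SAP*

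**What the plan says.** **Mechanism.** Section 16, item 4.3.1 (Overview) promises 300 "CGs randomly assigned in equal proportion to the experimental CG SOS Program or a usual care (UC) arm". The only method given is in item 6.1: "CGs will be randomized to either usual care or Caregiver SOS using a random number table", after consent and baseline. Item 13.1 confirms "This is a two-site study".

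**Who assigns.** Item 3.1: "Randomization group will be assigned by the PI, Research Coordinator, or Biostatistician". Item 4.3.1, B.1, with the stated aim of keeping the Research Assistants blind: "the Project Coordinator will use a random number table to inform each CG of their group assignment". The data-access list in Section 11, question 5 reads "1 Principal investigator; 3 Co-Investigators; 1 Care Manager; 1 Research Coordinator; 2 Research Assistants", with no Project Coordinator.

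**Who recruits and assesses.** Item 3.1: "Screening, research assessments, and chart reviews will be conducted by the Research Assistants and Research Coordinator", with the Care Manager added where appropriate. Item 6.2: "The Research Coordinator and Research Assistants (and, if needed, Care Manager) will be obtaining informed consent". Item 8.1 has the Research Coordinator conduct the qualitative interviews at the end of the 4-month visit; B.1 draws those 30 interviewees from the SOS arm.

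**Safeguards present.** B.1 places assignment after consent, screening and baseline, and has Research Assistants remind caregivers before each assessment not to reveal their arm.

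**The concern.** Two protections are at issue. The first is allocation concealment: nobody deciding whom to approach, how to conduct consent or whether a borderline caregiver qualifies should be able to know the next assignment. The second is assessor blinding: the K10, the primary outcome, is self-reported and mostly taken by telephone interview, so an interviewer who knows the arm can influence the answers.

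The plan aims at the second and does not describe the first. Under the roles as written, the Research Coordinator may assign, consent, screen and assess. Selection bias from a foreseeable sequence cannot be reliably repaired afterwards, because the planned covariate adjustment reaches only measured variables. Chance imbalance between arms or sites is a separate and smaller matter.

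**Working it through.** **Step 1. Roles side by side (Section 16 unless noted).**

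| Task | Permitted staff | Place |
|---|---|---|
| Assign arm | PI, Research Coordinator or Biostatistician | 3.1 |
| Use the table, inform caregiver | Project Coordinator | 4.3.1, B.1 |
| Obtain consent | Research Coordinator, Research Assistants; Care Manager if needed | 6.2 |
| Screen and assess | Research Assistants, Research Coordinator; Care Manager where appropriate | 3.1 |
| Screen, baseline and follow-up | Research Assistant only | 4.3.1, B.1 |
| Interview SOS caregivers at 4 months | Research Coordinator | 8.1 with B.1 |

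The Research Coordinator can appear in every task in 3.1 and 6.2. If the Project Coordinator is the same person, the overlap is direct. If not, 3.1 and B.1 disagree on who randomises. The two items also disagree on who assesses. A Research Coordinator who assigns, or who has interviewed a caregiver from the SOS arm, knows the arm at any later assessment of that caregiver. The Care Manager delivers SOS and so also knows it.

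**Step 2. Does the ordering in B.1 close the gap?** Assignment after baseline stops an arm being given before eligibility is settled. It does not stop someone with access to a readable sequence from knowing the next entry while approaching, consenting or screening the next caregiver. Enrolment is rolling (C.1) over 2.75 years (5.4), and the exclusion for impairments that hinder participation (7.1) needs judgement.

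**Step 3. Size of the balance issue.** The plan's own figures first (item 9.1): 300 × 0.80 / 2 = 120 per group, and 0.235 × 10 = 2.35 K10 points; both reproduce. The 0.235 SD itself depends on the correlation between the two follow-ups, which is not stated, so I take it as given. Assuming a two-sided 5% test:

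- MDES = (1.960 + 0.842) × √(2/120) × √V = 0.3617 × √V, so V = (0.235 / 0.3617)² = 0.422.

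If the table is used as simple 1:1 randomisation, the SOS count is Binomial(300, 0.5):

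- P(exactly 150:150) = 4.6%
- P(arms differ by 20 or more) = 27%
- P(arms differ by 30 or more) = 9.4%
- central 95% range: 133 to 167 in an arm

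Power at 0.235 SD with 240 completers split 167:133 (133.6 and 106.4):

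- SE = √0.422 × √(1/133.6 + 1/106.4) = 0.0844
- power = Φ(0.235 / 0.0844 − 1.960) = 79.5%, against 80.0% with equal arms
- MDES becomes 0.237 SD

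**Step 4. Site.** The split of the 300 between sites is not stated. Assuming the smaller site supplies 20% to 50%, the 95% bound on the between-arm difference in site share is 1.96 × √(2p(1 − p)/150), or 9 to 11 percentage points. If the sites differed by 3 K10 points (also an assumption), the raw follow-up contrast would move by about 0.09 × 3 = 0.27 to 0.11 × 3 = 0.33 points. The primary effect, β3 in item 9.2, is the treatment-by-follow-up term. A constant site difference falls into the baseline arm term β1 and largely cancels from β3; only a site difference in change over time would matter.

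**The case against.** The strongest reply is that the plan already does much of what is needed. Assignment follows eligibility and baseline, the Research Assistants are kept out of it, and many entry criteria are scored cut-offs. The PI and Biostatistician are alternative assigners whom the plan does not name as consenting or screening. All of this is correct. It narrows the risk but does not remove it, because the Research Coordinator remains a permitted assigner.

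Three stronger readings are tempting and go beyond the documents:

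- *The screener holds a visible list.* The plan does not say who keeps the table or whether it can be read ahead. The supportable statement is that concealment is not described.
- *There are no blocks or site strata.* This is inferred from silence. A random number table can generate permuted blocks, and the Data Analysis Plan (Appendix 4, cited in Section 4, item 7.1) was not available for this check.
- *The sites recruit from different services, so site will confound the result.* Item 3.1 draws on both sites' mental health clinics and Caregiver Support Programs and on VINCI; only the Behavioral Health Laboratory is specific to one site. Simple randomisation is unbiased, and the standard error covers chance imbalance.

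The absent Project Coordinator is also suggestive only: the Section 11 list covers data access, and the Biostatistician is missing from it too.

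**Conclusion.** The point holds for concealment and assessor blinding. Followed as written, the plan allows one person to recruit with foreknowledge of the next assignment, and allows someone who knows the arm to collect follow-up outcomes. The documents do not show that either will happen: the overlap is one of three permitted options, and its effect on the K10 cannot be sized from what is given.

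Balance is minor. A large arm difference is fairly likely under simple randomisation, but it costs about half a point of power even at the edge of the 95% range, and a site main effect would add little to β3. These figures rest on simple allocation, a two-sided test, the plan's 0.235 SD, and assumed site shares. The change is a cheap improvement; the gap does not by itself invalidate the trial.

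**What to change.** 1. Reconcile Section 16, item 3.1 with item 4.3.1, B.1: name one role that generates the sequence, one that releases assignments, and those that may assess.
2. Have the Biostatistician, already a permitted assigner, generate the list in permuted blocks of varying size within site. With blocks of at most 6, the arms could differ by no more than 3 per site, or 6 in all, when recruitment ends.
3. Hide the list from everyone who consents, screens or assesses, and release one assignment at a time once baseline is complete. REDCap is one option; the plan names it for data collection only, so its use for allocation and the access rights would need to be set up.
4. Bar anyone who assigns or knows the arm, including the Research Coordinator and Care Manager, from follow-up outcome assessments.
5. If Appendix 4 already covers any of this, cite it in items 4.3.1 and 6.1.

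The cost is set-up time, two lists to maintain and less flexible staffing of assessments. The sample size does not change.

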CMs also will enter clinical data into VA REDCap and the Behavioral Health Laboratory (BHL) software. The BHL software is a VA approved and network-wide installed software package that allows providers to track participants and to graphically display assessment reports. The software has been in use for more than 10 years in the VA. All REDCap and BHL data collection, transfer, and storage of data will be performed on the VA Intranet and thus access to the system is user based and requires maintenance of all relevant employee trainings. CR and CG- related VA and non-VA healthcare and service utilization will be obtained using VINCI or by self- report. When estimating non-VA utilization of care, we plan to follow HERC's guidebook which provides detailed documentation and suggestions for analyzing non-VA data on procedures.⁶⁸ The utilization database will include a "time window" variable spanning one year prior to and one year following the final CM call. Extracting clinical patient record data electronically to the greatest extent possible will improve validity and reduce respondent burden. Detailed procedures will be followed to protect against potential risks to privacy and breaches of confidentiality.

9. Data Analysis

9.1. Provide sample size determination and analysis (include anticipated rate of screen failures, study discontinuations, lost to follow-up etc.).

Power calculations were computed for Aim 1 based on 300 consenting CGs. Estimating a maximum of 20% attrition from follow-up (final n=120/group), typical correlation of .70 between baseline and each of two follow-ups, 5% significance tests, and 80% power, we will be able to find a minimum detectable effect size (MDES) of 0.235 standard deviations (SD). This is within the range of effect sizes found in other CG intervention studies.³⁷ For the primary outcome (Aim 1a) we expect a standard deviation for the K10 of about 10,⁵⁸ suggesting that we could detect a difference of 2.35 points between treatment and control based on mixed effects models. A clinically meaningful treatment-control difference of 3 points is well within the range of detectable differences. Similarly, for the secondary outcome measure (Aim 1b), a C-WLQ summary score improvement of lost productivity due to caregiving burden (SD=4.4%), will yield a MDES of 1.0%. Exploratory analyses will be underpowered.

9.2. Describe how, where and by whom the data will be analyzed.

All analyses will be run by the PI or Biostatistician.

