Power, Sample Size, and Missing Data: As described above, the MDES is 0.235 SD for 5% significance tests and 80% power with a starting sample of 300. Questionnaires will be administered by RAs using software that encourages response and does not permit multiple or out-of-range responses, for which missing data rates of 1-3% are typical and are easily resolved with multiple imputation techniques. While non-VA care will be assessed by self-report, VA claims databases are complete by design. We will conduct attrition analyses to assess differences in CG characteristics between those with complete vs. incomplete data. If differences are found, covariates will be included in final adjusted models. We acknowledge that we may be underpowered to address sample heterogeneity and moderators of treatment effect. Thus, to maximize the interpretability and utility of our findings, in addition to the models described below, the central tendency, variation and potential trends over time will be evaluated using means, standard deviations, and 75%, 85%, and 95% confidence intervals (CIs) plotted across time for each condition.⁷⁶ CIs will be interpreted with respect to clinically meaningful treatment group differences. Results from qualitative analyses also will be used to provide a context for treatment effects across potential moderators.

Preliminary Analyses: We will continually assess data quality and randomization success, testing for baseline group differences in key variables (e.g., gender, age, race/ethnicity, job flexibility, K10 and C-WLQ scores, and CR condition). If early analyses indicate group

differences, we will include the variables as covariates in the final adjusted models. We will review summary statistics (e.g., percentages, means and medians) to evaluate whether responses on the major variables (e.g., K10 distress score) are consistent with distributions obtained in other studies and psychometric performance is maintained (e.g., Cronbach's alpha statistics). We will apply appropriate transformations to highly skewed continuous variables. All preliminary analyses will be conducted using SAS version 9.3 (SAS Institute, Cary, NC).

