Specific Aims 1 and 2-Assessing Randomization Group Differences in Outcomes: In order to analyze the degree to which randomization group is associated with changes in our primary (CG distress) and secondary (CG work functioning) outcomes over time (Hyp 1a and 1b), we will run separate intent-to-treat, mixed effects linear regression models (using SAS PROC MIXED). Mixed models account for multiple observations (baseline and follow-up) and make use of all available data for each CG (regardless of drop-out or missing assessment periods). Specifically, we will specify a mixed effects model $Y_t = \beta_1 T + \beta_2 Z + \beta_3 TF + \beta_4 t + \epsilon$, where T is the indicator for treatment group (1 for SOS and 0 for UC), $t=0, 1, 2$ for baseline and the two follow-ups ($F=1$ for both), and Z is the vector for all other covariates and Y_t is the outcome score measured at time t . We will specify CG distress (K10 score) and CG work functioning (C-WLQ score), respectively, as dependent variables to test Hyp 1a and 1b. The overall treatment effect (improvement from the baseline) will be measured by β_3 . For exploratory purposes, we will test for the treatment trajectory difference by expanding the mixed model to estimate TF interactions separately for each time point.

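### Adding baseline-imbalanced variables as main-effect covariates does not correct the difference-in-change estimate; a baseline-adjusted primary model with a follow-up (F) or visit term should be prespecified

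*Combined protocol and SAP*

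**What the plan says.** All references are to the combined protocol and SAP, Section 16, items 9.1 and 9.2.

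- **Preliminary Analyses (9.2).** The arms are compared at baseline by "testing for baseline group differences in key variables", with the variables given as examples ("e.g., gender, age, race/ethnicity, job flexibility, K10 and C-WLQ scores, and CR condition"). The action on finding a difference is that "differences, we will include the variables as covariates in the final adjusted models". No test level and no closed list are given.
- **Power, Sample Size, and Missing Data (9.2).** A parallel rule covers attrition: "If differences are found, covariates will be included in final adjusted models".
- **Specific Aims 1 and 2 (9.2).** The model is Y_t = β1·T + β2·Z + β3·TF + β4·t + ε, with t = 0, 1, 2 and F = 1 at both follow-ups. Baseline is therefore one of the modelled outcome rows. "Z is the vector for all other covariates", and it enters once, with no interaction with F or t. "The overall treatment effect (improvement from the baseline) will be measured by" β3.
- **Sample size (9.1).** "Estimating a maximum of 20% attrition from follow-up (final n=120/group), typical correlation of .70 between baseline and each of two follow-ups", with 300 caregivers, K10 SD about 10, C-WLQ SD 4.4%, 5% tests and 80% power, giving an MDES of 0.235 SD (2.35 K10 points).

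The plan states no covariance structure, no follow-up-only ANCOVA, no constraint of equal arm means at baseline, and no different form for the final adjusted models.

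**The concern.** The rule exists to deal with chance imbalance. In this model the covariate it adds cannot reach the coefficient that is reported as the treatment effect. Readers of an adjusted result would believe the imbalance had been handled when the estimate is essentially the same number.

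β3 already subtracts the whole baseline difference. Regression to the mean calls for subtracting only the correlated part, so β3 over-corrects. The shift favours SOS when SOS starts with the higher distress score and favours usual care when SOS starts lower.

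A related gap makes the choice of model matter more. The printed equation has a linear time term and no F main effect, so a fall common to both arms that is not linear in visit number leaks into β3.

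**Working it through.** **Inputs.** From the plan: 150 per arm (300, equal allocation), K10 SD 10, r = .70 between baseline and each follow-up, 20% attrition, 5% and 80%. Assumed: two-sided tests; .70 also between the two follow-ups (compound symmetry); an intercept in the model; and, unless stated otherwise, dropout of 20% at 9 months with half of those also missing 4 months.

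**1. The plan's own figure.** GLS with a free arm term and visit effects, 150 baseline rows per arm and 120 per arm at both follow-ups, gives an MDES of 0.238 SD against the stated 0.235 (power 79.1% at 0.235). That is close enough to treat a difference-in-change model with visit effects as consistent with the power statement. With the dropout pattern above the MDES is 0.230.

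**2. What Z does to β3.** Split a time-constant Z into its arm means and its within-arm part. The arm means lie in the span of the intercept and T. The within-arm part is orthogonal to every arm-by-time term. So Z can move β1 but not β3.
- Complete data: β3 with and without baseline K10 in Z agrees to about 1e-12, including under arbitrary fixed covariance matrices and for an arbitrary Z.
- 20% random dropout, 6,000 simulated null trials: the mean absolute change in β3 is 0.066 points (printed) and 0.079 (with F), against SEs of 0.73 and 0.82. The slope of β3 on the imbalance is −0.234 without Z and −0.235 with Z (printed), and −0.295 and −0.297 (with F).

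**3. What remains, with F in the model.** Given imbalance d, the expected null difference at follow-up is r·d, while β3 subtracts d. The shift is −(1 − r)d = −0.30d. For r = .80, .60 and .50 it is −0.20d, −0.40d and −0.50d.
- SD of the imbalance: 10 × √(2/150) = 1.155.
- Mean |d|: 1.155 × √(2/π) = 0.92; shift 0.30 × 0.92 = 0.28 points.
- Just significant: 1.96 × 1.155 = 2.26; shift 0.30 × 2.26 = 0.68 points, which is 29% of 2.35. The range is 0.45 to 1.13 for r = .80 to .50.
- C-WLQ: 1.96 × 4.4 × √(2/150) = 1.00 percentage point; shift 0.30, against a stated MDES of 1.0%.

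**4. Conditional rejection under the null (with F, 20% dropout).** The critical value is 1.96 × 0.819 = 1.605 and the conditional SD is 0.743. At d = 2.26, the upper tail is at (1.605 − 0.679)/0.743 = 1.25 and the lower tail at (1.605 + 0.679)/0.743 = 3.07, giving 10.7% in total. At d = 0 it is 3.1%, and at d = 0.92 about 4%.

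**5. The printed equation, linear t and no F.** With complete data, β3 weights the cell means at baseline, 4 and 9 months by (0.6, 0, −0.6) in usual care and (−1, 0.8, 0.2) in SOS. An assumed common 3-point drop at both follow-ups gives 1.8 − 3.0 = −1.2 with no treatment effect. With SE 0.693 that rejects 41% of the time. The conditional shift is −0.24d. A constrained-baseline model without F still gives −1.0 (SE 0.632, 35% rejection). With F, both models give 0.

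**6. Precision under 20% dropout (K10 points).**

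| Model | SE | MDES (SD) |
|---|---|---|
| Printed | 0.734 | 0.206 |
| Free arm term, with F | 0.819 | 0.230 |
| Constrained baseline, with F | 0.743 | 0.208 |

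The constrained-baseline model with F has no shift at any d.

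**The case against.** **The contrast is valid and the error rate is intact.** With F, this stands. Difference in change is a legitimate estimand contrast, it is unbiased over randomisations with about 5% error, and it roughly meets the stated MDES. A reader might infer that the primary test is biased or inflated overall because of the covariate rule. The documents do not support that: small imbalances reject less than 5% of the time and offset the large ones. The 10.7% applies at exactly 2.26 points, which randomisation reaches or exceeds in about 5% of trials. But the plan itself chooses to act on observed imbalance, so behaviour given imbalance is a fair test of its rule.

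**An outcome's own baseline may not be meant for its own model.** Also fair. The plan gives one list for two models, and baseline K10 could be intended only for the C-WLQ model and the reverse. A reader might take it as settled that K10 enters the K10 model; the text does not say so. The result does not depend on it: no main-effect covariate moves β3 materially, and the over-correction comes from the change contrast under Specific Aims 1 and 2.

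**Deleting the trigger would be enough.** It would not. The shift remains with or without the trigger.

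**The attrition rule is equally faulty.** That goes too far. Covariates that predict dropout can help a mixed model; the only reservation is that they too are chosen after testing.

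**Conclusion.** The point holds as a conditional and efficiency problem, not as a failure of overall error control. The baseline-test rule does not correct the imbalance that triggers it. With F in the model, β3 over-corrects by about 0.30d, from about 0.28 points at a typical imbalance to 0.68 at a just-significant one.

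The unconditional reassurance depends on an F or visit term. As printed, the equation lacks it unless the common time course is flat or linear in visit number. A common early fall is plausible because item 7.1 requires a positive distress screen, but the 3-point figure is an assumption.

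All figures rest on compound symmetry with r = .70; only r has been varied, and item 9.2 elsewhere mentions terms (β5, and a random β6t) that the printed equation lacks. The change is worth making, but the primary analysis is not invalid for want of it if F is included.

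**What to change.** **In Specific Aims 1 and 2:**
- Require an F main effect or categorical visit, and state the covariance structure.
- Prespecify a baseline-adjusted primary model for K10 and for C-WLQ. Use either a constrained-baseline mixed model (arm means equal at t = 0) with visit effects, or the two follow-ups as outcomes with the baseline outcome as covariate and a visit effect.
- Do not enter an outcome's own baseline in Z while it is also the t = 0 row, and do not use a version without F.

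**In Preliminary Analyses:**
- Delete the baseline-test trigger.
- Name a short fixed covariate list from items already collected, for example site, care-recipient condition, job flexibility, and caregiver age, gender and race/ethnicity.
- Keep prespecified predictors of dropout in the model, and put any covariate found later by testing in a sensitivity analysis.

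Both parts are needed. The cost is SAP wording and a few degrees of freedom, with no new data. Relative to the free-arm model with F, the SE falls by about 9% (0.743/0.819 = 0.907). Relative to the printed model it is about equal (0.743 against 0.734), so the protection against a common time course costs almost no precision.
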